## **Procedures**

A cohort of 15 children and adolescents with diabetes will be recruited for the study. We hypothesize that glucose concentration collected from interstitial fluid will correlate with both capillary blood glucose (collected from a lancet and measured with a BGMD) and venous glucose (collected from an intravenous

catheter). In this aim, we will measure glucose concentrations collected from children and adolescents with diabetes (type 1 or type 2).

Glucose measurements from all three methods (interstitial fluid - microneedle, capillary blood - lancet, and venous blood - intravenous catheter) will be made simultaneously from each subject every hour from 8:30 AM – 11:30 AM. Suction (up to 500 mmHg) may be applied after microneedle treatment at the skin site for up to 1 hour to withdraw fluid ( $\leq 500 \mu\text{l}$  [microliters]) from the skin. Measurements will be taken every hour for the study period. Subjects will arrive in the morning after an overnight fast and will eat or drink a breakfast during the study visit. Subjects will be asked about the pain and apprehension with each device.

Pain and apprehension will be determined with the use of the visual analog pain scale (VAS) and a questionnaire. Each subject will be asked to rate their apprehension prior to receiving each method for blood or interstitial fluid collection as well as the pain associated with each method immediately after collection. Each subject will receive each method of glucose monitoring simultaneously. Similar to a cross-over study, each subject's apprehension, pain, and glucose with each method will be compared using the paired t-test method. Sample size is determined based on the number of subjects needed to achieve statistically significant differences in pain based on the VAS. In order to detect a pain difference of 20 mm with a standard deviation of 20 at a power of 95% and an alpha of 0.05, 15 subjects will be recruited.

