### Expected Outcomes

In this study, we will develop microneedle patches for collection of interstitial fluid for subsequent measurement of glucose concentration in an effort to improve patient compliance and cost (Fig 1). Recent studies have shown that intradermal microneedle insertion is less painful and strongly preferred by patients receiving drug delivery through injections [13-15]. We hypothesize that interstitial fluid collection using microneedle patches can improve glycemic monitoring in being as effective as conventional methods and in a less painful manner, thereby improving patient compliance. The microneedle patches will be fabricated at the Global Center for Medical Innovation at the Georgia Institute of Technology. Prior to use in human subjects, the microneedle patches will be sterilized by an approved sterility center.

**Fig. 1. Microneedle patches for interstitial fluid glucose monitoring. Prototype patches are shown with green dye in the microneedles for visual enhancement (left). Application of microneedle patches to the skin is simple (center). High magnification images of microneedles (right).**

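### Breakfast has no stated place among the hourly rounds and no analysis by time since the meal is specified, so the signed mean glucose difference may vary with meal time and may hide partly cancelling errors

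*Combined protocol and SAP*

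**What the plan says.** All the design text on this point is in the Procedures section.

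- Meal: "Subjects will arrive in the morning after an overnight fast and will eat or drink a breakfast during the study visit". No clock time, position among the rounds or meal duration is given.
- Rounds: measurements by all three methods "will be made simultaneously from each subject every hour from 8:30 AM – 11:30 AM". That makes four rounds per child if both ends count.
- Interstitial sampling: "Suction (up to 500 mmHg) may be applied after microneedle treatment at the skin site for up to 1 hour". The permitted collection time is therefore as long as the gap between rounds.
- Analysis: "Similar to a cross-over study, each subject's apprehension, pain, and glucose with each method will be compared using the paired t-test method". The text does not say whether the hourly values are averaged within a child, entered as separate pairs or tested round by round. It describes no analysis by round or time since the meal, no absolute-error measure and no limits of agreement.
- Aims: the glucose hypothesis is one of correlation ("We hypothesize that glucose concentration collected from interstitial fluid will correlate with both capillary blood glucose"). The Expected Outcomes section adds that the patches "can improve glycemic monitoring in being as effective as conventional methods and in a less painful manner", with no accuracy margin.

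**The concern.** A paired t-test on glucose tests a mean signed difference. If interstitial glucose follows blood with any delay, the delay has no effect while glucose is steady, makes the interstitial reading low while glucose rises and makes it high while glucose falls. The visit is built to contain both a fasting and a post-meal state, but the mix of states in each child is left open. Nothing guarantees that every child has at least one round of each kind.

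Two distinct consequences follow. First, the mean difference for a child would reflect when the child ate as well as any bias of the method. Second, a small, non-significant mean could be read as support for the effectiveness aim although individual post-meal readings were off. The second consequence comes from using a signed mean without a measure of agreement, so it would remain even if every child ate at the same time.

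**Working it through.** **The plan's own figure.** The only calculation in the plan is for pain: "detect a pain difference of 20 mm with a standard deviation of 20", power 95%, alpha 0.05, 15 subjects. The paired formula gives n = ((1.960 + 1.645) × 20/20)² = 12.99, so 13. Exact two-sided paired-t power at n = 15 is 94.9%, if 20 is the SD of the paired differences. The figure reproduces but says nothing about glucose.

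**Inputs for the illustration.** From the Procedures section: rounds at 0, 60, 120 and 180 min after 8:30, with breakfast time open. Assumed, because the documents give neither: the glucose curve and the lag. Differences are interstitial minus blood, in mg/dL, and a child's mean is taken over the four rounds. That averaging is also an assumption.

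**Model A: fixed delay.** Glucose rises 100 over 60 min after breakfast, then falls 0.8 per min. With delay d, a fasting round differs by 0, a rising round by −(100/60)d and a falling round by +0.8d. For d = 10 these are 0, −16.7 and +8.0.

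- Breakfast at 8:45: mean (0 − 16.7 + 8.0 + 8.0)/4 = −0.2; mean absolute (16.7 + 8.0 + 8.0)/4 = 8.2.
- Breakfast at 10:40: mean (0 + 0 + 0 − 16.7)/4 = −4.2.
- The shift between these two times is 4.0. It scales with d: 4.0 × 5/10 = 2.0 at 5 min and 4.0 × 15/10 = 6.0 at 15 min.

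**Model B: first-order lag.** Blood is B = 120 + 100·x·e^(1−x), where x is minutes since breakfast divided by 60. Interstitial glucose I follows dI/dt = (B − I)/τ. For τ = 10 min:

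| Breakfast | Four round differences | Mean | Mean absolute |
|---|---|---|---|
| 8:35 | 0, −5.9, +5.7, +5.0 | +1.2 | 4.2 |
| 8:45 | 0, −10.8, +5.2, +5.4 | −0.1 | 5.3 |
| 9:35 | 0, 0, −5.9, +5.7 | 0.0 | 2.9 |
| 10:05 | 0, 0, −22.7, +2.9 | −5.0 | 6.4 |
| 11:05 | 0, 0, 0, −22.7 | −5.7 | 5.7 |

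With breakfast uniform over 8:30 to 11:30, the child means spread as follows.

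| Lag τ | Range of child means | Width | SD between children |
|---|---|---|---|
| 5 min | −3.9 to +1.1 | 5.0 | 1.3 |
| 10 min | −6.4 to +1.7 | 8.1 | 2.3 |
| 20 min | −10.3 to +1.1 | 11.4 | 2.8 |

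For τ = 10 min the average child mean is −3.0 and the average mean absolute difference is 5.2.

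**Suction as the offset, with no physiological lag.** On the Model A curve, suppose the interstitial sample averages the hour before the blood draw. Breakfast at 8:45 gives 0, −46.9, +19.4 and +24.0: mean −0.9, mean absolute 22.6. Breakfast at 10:40 gives a mean of −12.2. If suction follows the draw instead, the 8:45 breakfast gives a mean of −0.2 and a mean absolute difference of 18.5. These are full-hour cases, the longest that the plan allows.

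**Can hourly values identify rising and falling rounds?** Not reliably. In Model A with breakfast 45 min after the first round, blood is 100 × 15/60 = 25 above baseline at 60 min and 100 − 0.8 × 15 = 88 at 120 min. The second value is higher although glucose has already been falling for 15 min. Comparing it with the previous round would label it rising.

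**The case against.** The strongest reply has four parts.

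1. A reader might infer that all rounds are pooled. The text does not say so. Testing each round separately would fit the wording and would stop errors from cancelling across rounds within a child. This stands: the supportable statement is that no analysis by round or time since the meal is specified.

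2. A reader might infer that each child's difference must depend on breakfast time. That needs an offset between interstitial fluid and blood. The documents give no lag, and with no lag and truly simultaneous sampling the effect is zero. This stands too. The permitted hour of suction is the only source of an offset in the documents, and its actual length may be shorter.

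3. A reader might infer that a near-zero mean is the expected result. It depends on the curve. With Model A, breakfast at 8:45 and a 10-min delay, a fall of 0.4 per min gives a mean of −2.2, a 45-min rise gives −1.6, a 120-min rise gives −2.2, and a 90-min rise with a fall of 1.2 gives +3.2. Varying only the delay scales all terms together and so does not test this. A late breakfast gives a one-sided negative error with little or no cancellation. Dependence on timing can also be weak: in Model A any breakfast from 0 to 50 min after the first round gives the same −0.2. Partial cancellation survives: with the fall of 0.4, for example, the mean of −2.2 compares with a mean absolute difference of (16.7 + 4.0 + 4.0)/4 = 6.2.

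4. The study is sized on pain, its glucose hypothesis is correlation, and no glucose margin exists against which a few mg/dL could be judged. This limits the weight of the point. It does not remove it, because the plan also compares glucose by paired t-test and aims to show effectiveness equal to conventional methods.

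**Conclusion.** The point holds as a conditional one. The plan leaves the place of breakfast open and specifies no analysis by round or time since the meal. If interstitial readings trail blood or average it over time, the signed mean difference varies with breakfast time and can partly hide opposite errors.

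Across the two assumed curves, the shift in a child's mean is roughly 4 to 11 mg/dL for most of the lags tried; the mildest case, a fixed 5-min delay, gives 2. With a 10-min lag, a mean near zero can accompany a mean absolute difference of about 3 to 8 mg/dL. Every one of these sizes rests on an assumed curve, an assumed lag and averaging over four rounds. The documents do not show that any such error will occur. The cancellation concerns the paired t-test only and does not affect the correlation hypothesis. The change is worth making before data collection because it is cheap and the breakfast times cannot be recovered reliably afterwards.

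**What to change.** - Record the clock time at which each child starts breakfast. State where breakfast falls relative to the rounds, as the investigators decide, so that every child contributes both fasting and post-breakfast rounds.
- Prespecify interstitial-minus-venous and interstitial-minus-capillary differences separately for fasting and post-breakfast rounds. Define the post-breakfast rounds by time since the meal, not by a rising or falling label taken from hourly values.
- Add a mean absolute difference or limits of agreement, by a method that allows for repeated rounds within a child. Settling the meal time alone is not enough: in the 8:35 row of Model B, an illustration only, the mean is +1.2 against a mean absolute difference of 4.2.
- State how the hourly values enter the paired t-test.

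The cost is one recorded time per child, one more table, and wider intervals within each phase because each uses fewer pairs.

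### The order of the three collection methods is not stated, so a habitual order would confound method with position in the pain and apprehension comparisons

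*Combined protocol and SAP*

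**What the plan says.** All of the relevant text is in the Procedures section of the combined protocol and SAP.

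- **Timing of glucose samples.** Measurements by all three methods "will be made simultaneously from each subject every hour from 8:30 AM" until 11:30 AM.
- **Timing of the methods.** "Each subject will receive each method of glucose monitoring simultaneously".
- **Timing of ratings.** Beforehand, every child must "rate their apprehension prior to receiving each method for blood or interstitial fluid collection". The pain rating comes at the other end of the procedure, and the plan adds it with the words "as well as the pain associated with each method immediately after collection".
- **Methods.** The comparators to the microneedle are "capillary blood - lancet, and venous blood - intravenous catheter". Suction "may be applied after microneedle treatment at the skin site for up to 1 hour".
- **Analysis.** The design is called "Similar to a cross-over study", and each child's "apprehension, pain, and glucose with each method will be compared using the paired t-test method".
- **Sample size.** Fifteen children, for a VAS pain difference of 20 mm with a standard deviation of 20, power 95% and alpha 0.05.

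The section gives no order for the methods within a session, no spacing between them, no randomisation or counterbalancing, and no order term. It does not say which of the hourly sessions are rated.

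**The concern.** A rating before each method and another straight after it make sense only if the methods are separate events. The natural reading is therefore one hourly session with the methods taken one after another. On that reading something must come first, and the plan leaves the choice to whoever runs the session.

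A child's rating of the second or third procedure may depend on what has just happened, through sensitisation, habituation, relief or comparison with the procedure before. A paired t-test removes stable differences between children. It does not remove a shift that all children share because one method always came earlier. In a cross-over trial, randomised order gives that protection, and here it is absent. What is at stake is the outcome on which the trial is sized, together with apprehension. A habitual order could create a pain difference between methods that are equally painful, or hide a real one.

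**Working it through.** **Inputs from the Procedures section:** n = 15, difference 20 mm, SD 20 mm, alpha 0.05, paired t-test. **Assumptions:** a two-sided test; SD 20 read as the SD of the paired differences; order shifts of 2, 5 and 10 mm, which have no source in the documents.

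**1. The plan's own figure.** Noncentrality = (20/20) × √15 = 3.873, with 14 degrees of freedom and critical value 2.145. Power from the noncentral t is 94.9%. This agrees with the stated 95%, so the sample size is not in dispute.

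**2. All 15 children share one order.** A shift of b mm moves every paired difference by b, so the bias is b and the SD is unchanged. With no true difference, noncentrality = (b/20) × √15. With a true 20 mm and the shift against it, noncentrality = ((20 − b)/20) × √15.

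| Assumed shift | Noncentrality, no true difference | False-positive rate | Noncentrality, true 20 mm | Power |
|---|---|---|---|---|
| 0 mm | 0 | 5% | 3.873 | 94.9% |
| 2 mm | 0.387 | 6.5% | 3.486 | 90% |
| 5 mm | 0.968 | 14.7% | 2.905 | 77% |
| 10 mm | 1.936 | 43.8% | 1.936 | 44% |

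**3. Order varies between children.** If k children have one order and 15 − k the reverse, the bias is b × (2k − 15)/15. For example, with k = 12 and b = 5 it is 5 × 9/15 = 3 mm. The rates below are from simulation of the unadjusted paired t-test.

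| Children sharing one order | Shift | Bias | False-positive rate | Power, shift against 20 mm |
|---|---|---|---|---|
| 12 | 5 mm | 3.0 mm | 8% | 85% |
| 12 | 10 mm | 6.0 mm | 15% | 65% |
| 10 | 5 mm | 1.7 mm | 5% | 90% |
| 10 | 10 mm | 3.3 mm | 6% | 79% |
| 8 | 5 mm | 0.3 mm | 4% | 93% |
| 8 | 10 mm | 0.7 mm | 3% | 89% |

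The false-positive problem is essentially gone once 10 or fewer share an order. What remains is some loss of power, because the unmodelled shift adds variance.

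**4. Cost of controlling order.**

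- *Three methods.* Take three copies of a three-sequence Latin square (ABC, BCA, CAB; 9 children) and two of its mirror image (CBA, ACB, BAC; 6 children). Each method falls 3 + 2 = 5 times in each position. Each ordered neighbour pair occurs 3 × 2 = 6 or 2 × 2 = 4 times. Regressing a pairwise difference on an intercept and two position terms leaves the variance factor at exactly 1/15, with 12 degrees of freedom. Power for 20 mm is 94.4%.
- *Two methods, 8:7, with an order term.* The variance factor is (1/8 + 1/7)/4 = 0.0670 against 1/15 = 0.0667, so noncentrality is 3.864 with 13 degrees of freedom. Power for 20 mm is 94.6%.

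**The case against.** The strongest reply is that this is a 15-child first assessment, that the cross-over remark most naturally describes within-child pairing and makes no claim of randomised sequences, and that no document shows an order effect exists. Much of that stands. The size and direction of any bias cannot be derived, a 2 mm shift does little harm, and staff may vary the order without being told to. It does not remove the point, because order cannot be randomised after the data are collected and prevention costs half a percentage point of power.

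A reader might infer three stronger claims that the text does not support.

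- **That venous collection must always be rated first because a catheter has to be in place.** Pain is rated after collection. With an indwelling catheter, collection is the draw, which can fall anywhere in the session. The inference needs insertion to be the rated event, and the plan does not say so.
- **That suction puts the microneedle last.** Suction is optional, and the plan does not say whether it counts as collection. A late rating fixes when the rating is taken, not when the patch was applied.
- **That ratings cannot be attributed to a method because all three act at once.** The per-method rating times point to the methods being taken in turn. No figure in the documents would support an estimate of spill-over between ratings. What is left is a conflict of wording.

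For the glucose comparison, simultaneous sampling within a session is reasonable and is not criticised here.

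**Conclusion.** The point holds as a design gap that should be fixed, with medium confidence. The sentence on simultaneous methods conflicts with the rating times. On the likelier reading nothing stops method from being confounded with position in the pain and apprehension comparisons. The harm is conditional. It is serious only if nearly all children share one order and the shift is a sizeable fraction of the 20 mm target. At the extreme shown (10 mm, all 15 alike) the false-positive rate and the power are both about 44%; at 2 mm they are 6.5% and 90%. These figures rest on assumed shifts and on SD 20 being that of the paired differences. If a study manual or a page outside the public text already fixes or randomises the order, the point narrows to reconciling the wording and matching the analysis.

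**What to change.** 1. State that simultaneous means within the same hourly session, for the glucose comparison.
2. In each rated session, take the methods one after another and complete each rating before the next method begins. Say which sessions are rated.
3. Randomise the order per child from a prepared 15-line list, for example the 9 + 6 Latin-square arrangement above. Record the order used and the clock time of every sample and rating.
4. Include position in the pain and apprehension analyses.
5. Keep the plan's rating times, and state whether suction and catheter insertion belong to the rated collection.
6. If the venous position cannot be varied, randomise microneedle versus lancet 8:7 with an order term. State that venous pain and apprehension comparisons remain confounded with position.

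**Cost.** A short list, some protocol wording, and samples a few minutes apart in rated sessions. The gap would be longer if suction, which the plan allows for up to an hour, is counted as collection, so item 5 must be settled first. Power for 20 mm is 94.4% (three methods) or 94.6% (two methods) against 94.9%, with no extra children. Neighbour pairs are nearly but not exactly balanced at 15; exact balance needs a multiple of six.

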Microneedles have been developed to create transport pathways for small drugs, macromolecules, and fluid flow in a painless manner. They range in length from 150 – 900  $\mu\text{m}$  and the microscopic length permits appropriate collection of interstitial fluid but limits the extension into the abundant nerve-ending region of the dermis, thereby minimizing pain [9-11]. We have collected interstitial fluid with subsequent glucose measurements using hollow, glass microneedles previously however, it required a two-step process [12]. Hollow, glass microneedles were applied to human skin and suction was required to withdraw the interstitial fluid from the needles. The study showed a strong correlation between glucose levels in interstitial fluid and blood but, the two-step process was time-consuming and cumbersome, making it difficult to translate it into a point-of-care system.

The American Diabetes Association (ADA) recommends that diabetics maintain their plasma glucose in a strict range to prevent long-term complications of diabetes [13]. Children with diabetes who fail to appropriately monitor their blood glucose are not aware of how to adjust their diet and/or pharmacotherapy to optimize their glycemic control. In this project, we propose to target collection of interstitial fluid for glucose measurement from the painless application of solid microneedles in children with diabetes. Because these microneedles and continuous indwelling sensors for interstitial fluid glucose monitoring are both FDA-approved, this is a well-established and accepted medium from which to sample and measure glucose [6, 8].

Needle anxiety prevents ideal glycemic control and up to 50% of children and adolescents fail to monitor their blood glucose consistently [7, 14]. Microneedle patches could eliminate needle anxiety and improve adherence to proper glucose monitoring. Studies show microneedles reduce injection pain [9, 10] and increase patient and clinician acceptance for other injected drugs [15]. We will investigate if microneedle patches can improve adherence and compliance with glucose monitoring in children and adolescents with diabetes.

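### The stated hypothesis is that interstitial glucose correlates with blood glucose, but the only glucose analysis named in the available text is a paired t-test, which addresses average bias and not correlation

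*Combined protocol and SAP*

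**What the plan says.** The glucose hypothesis is in Procedures: "We hypothesize that glucose concentration collected from interstitial fluid will correlate with both capillary blood glucose", and the sentence goes on to include venous glucose. Readings by all three methods "will be made simultaneously from each subject every hour from 8:30 AM – 11:30 AM", which is four time points per child if both ends count. The same section names the analysis: "apprehension, pain, and glucose with each method will be compared using the paired t-test method". It does not say how the hourly readings enter that test.

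Glucose plays no part in fixing the number of children: "Sample size is determined based on the number of subjects needed to achieve statistically significant differences in pain based on the VAS".

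Two other places bear on the point. Expected Outcomes adds a broader hypothesis, that the patch "can improve glycemic monitoring in being as effective as conventional methods and in a less painful manner". Background reports of earlier work with glass microneedles that "The study showed a strong correlation between glucose levels in interstitial fluid and blood"; this describes a past result and is not an analysis planned here. The available text names no correlation coefficient, regression, agreement analysis, equivalence margin or model for repeated readings.

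**The concern.** The hypothesis and the named test concern different quantities. Correlation asks whether interstitial glucose rises and falls with blood glucose. The paired t-test asks whether the average difference is zero. Correlation affects the variance of the difference, and so the power of the t-test, but it is not what is tested. Positive and negative errors also cancel in the mean, so individual readings can be far apart while the average difference is near zero.

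At stake is the study's first stated hypothesis. As written, it could be left without a pre-specified analysis able to test it, and the method would then be chosen after the data were seen. The silence on the hourly readings adds a second risk: treating them as independent pairs would give a t-test with the wrong error rate.

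**Working it through.** **The plan's own figure.** The only numerical design figure is for VAS pain: difference 20 mm, SD 20, power 95%, alpha 0.05, 15 children. Reading SD 20 as the SD of the paired difference and the test as two-sided, the normal approximation is n = ((1.960 + 1.645) / (20/20))² = 12.99, so 13. The exact paired t-test needs 16, and its power at n = 15 is 94.9%. The stated 15 is therefore reproduced closely, but it says nothing about glucose.

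**Inputs for glucose.** From Procedures: 15 children, hourly readings, paired t-test. Assumed, because the documents give no glucose SDs: every SD and offset below, in mg/dL, and four usable readings per child unless stated. Tests are two-sided at 0.05; simulations use 20,000 trials per setting.

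**Step 1. One value per child, SD 60 for each method.**

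| True r | True bias | t-test significant | Pearson test significant |
|---|---|---|---|
| 0 | 0 | 5.0% | 4.9% |
| 0.5 | 0 | 5.0% | 49.7% |
| 0.95 | 0 | 4.8% | 100% |
| 0.95 | 20 | 96.7% | 100% |

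The first three rows look alike to the t-test. The last row shows the converse: a strongly correlated method is declared different because of its bias (72% to 100% of trials as the assumed SD goes from 90 to 30).

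**Step 2. Four readings per child, t-test on child means, equal true means.** Between/within-child SDs are 40/40, 60/40 and 30/60.
- Unrelated readings: t-test significant in about 5%; within-subject correlation significant in about 5%.
- Readings that track blood glucose with independent errors of SD 5 to 15 and no time lag (mean within-subject r about 0.93 to 0.996): t-test still about 5%; within-subject correlation 100%.

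**Step 3. The same unrelated readings, all 60 pairs pooled as independent.** The within-child correlation of the differences is ICC = between² / (between² + within²). The variance of the overall mean is understated by about 1 + 3 × ICC, so the rejection rate is about 2 × [1 − Φ(1.96 / √(1 + 3 × ICC))].

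| Between/within SD | ICC | 1 + 3 × ICC | Approximate rejection | Simulated |
|---|---|---|---|---|
| 40/40 | 0.50 | 2.50 | 21.5% | 22% |
| 60/40 | 0.69 | 3.08 | 26.4% | 27% |
| 30/60 | 0.20 | 1.60 | 12.1% | 12% |

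The nominal rate is 5%.

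**Step 4. Individual disagreement.** With mean error zero and one value or mean per child, the t-test is non-significant in about 95% of trials whatever the error SD. The limits of agreement are ±1.96 × SD: ±39, ±59 or ±78 mg/dL at error SD 20, 30 or 40.

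**Step 5. What a within-subject correlation can deliver.** df = 15k − 15 − 1 for k readings per child. On the Fisher z scale, SE = 1/√(df − 1).
- k = 4: df = 44, SE = 0.1525. Power at r = 0.40 is Φ(0.4236/0.1525 − 1.96) = Φ(0.82) = 79%. An observed 0.80 has the interval tanh(1.0986 ± 0.2989) = 0.66 to 0.88.
- k = 3: df = 29, SE = 0.1890. Power is Φ(0.28) = 61%, and the interval is 0.62 to 0.90.

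**The case against.** The strongest reply is that this is an omission and not a wrong choice. Procedures says that glucose will be compared across methods by t-test; it does not say that the t-test will test the correlation hypothesis. Comparing means is legitimate and informs on bias. This stands, and the t-test's information should be kept. What remains is that the hypothesis has no named analysis.

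A second reply is that this is a small study powered on pain, and the investigators would compute a correlation anyway. The plan does not say so, nor how it would handle repeated readings, which Step 3 shows is not a detail.

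A third is that a within-child correlation has its own weakness. Every child moves from an overnight fast to breakfast during the visit, so it may partly reflect a shared meal-driven rise. This also stands, as does the point that the 100% in Step 2 assumes independent errors and no lag.

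Three stronger readings are tempting but not supported:
- That a non-significant t-test will be taken as proof of equal effectiveness. Nothing in the text says this; one can say only that such a result could not support the Expected Outcomes hypothesis, for which no margin is visible.
- That the t-test is non-significant in 95% of trials without condition. That requires one value or mean per child.
- That no correlation analysis exists anywhere. Parts of the document were not available, so this cannot be asserted.

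**Conclusion.** The concern holds for the available text. The correlation hypothesis is paired with a test of mean difference, and that mismatch does not depend on any assumed SD. With one value or mean per child and equal true means, the t-test gives about 5% significant results for unrelated and for almost perfectly correlated readings alike. Pooling the hourly pairs would add a validity problem, with about 12% to 27% rejection for unrelated readings of equal mean; that range rests on the assumed SDs and on four usable readings per child. The plan neither announces nor excludes pooling. Sample timing and the broader effectiveness hypothesis are secondary.

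**What to change.** In Procedures, keep the paired t-test for pain and apprehension. For glucose, specify the following for microneedle versus venous and for microneedle versus capillary:
- a correlation analysis that allows for repeated readings within a child, for example repeated-measures correlation, with its 95% CI and a statement that it may partly reflect the shared rise in glucose after breakfast;
- the mean paired difference with a 95% CI, using the child as the unit or a subject effect;
- 95% limits of agreement with a subject effect, because neither of the first two shows individual disagreement.

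State that the hourly pairs will not be treated as independent.

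Two secondary changes. First, record actual collection times and pair readings by them, because "Suction (up to 500 mmHg) may be applied after microneedle treatment at the skin site for up to 1 hour to withdraw fluid". If collection takes the full hour, its midpoint is 30 minutes after the start; glucose changing at an assumed 0.5 to 2 mg/dL per minute would move 15 to 60 mg/dL in that time. Analysis cannot fully repair this, so it should be stated as a limitation. Second, state that a non-significant t-test will not be read as showing that the patch is as effective as conventional methods. An equivalence claim would need a margin fixed in advance, which is a clinical decision.

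The cost is a little more analysis work and a record of times, with no new children or samples. Precision will be limited, as Step 5 shows for the correlation. For agreement, at an assumed error SD of 40 (true upper limit 78 mg/dL) and four readings per child, the estimated upper limit would fall between about 62 and 98 in 95% of trials if errors are independent within a child, and between about 54 and 103 at a within-child error correlation of 0.5.
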